12.4.4 Statistical Analysis of Pharmacodynamic Parameters

Pharmacodynamic parameters of serum total calcium, albumin-corrected calcium and phosphate and calcium-phosphate product will be listed and summarized with descriptive statistics (number, arithmetic mean, SD, CV%, median, minimum, maximum, geometric mean, and geometric CV%) by ethnic group, dose and time point. This will be done for both original and baseline-adjusted values.

Box-Whisker plots for AUC_{last} and E_{max} based on both original and baseline-adjusted concentrations will be prepared for the 100 μ g dose with the Japanese cohort and Non-Japanese cohort side by side.

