2.2.2 Secondary Objectives

- To assess the dose proportionality of the PKs of rhPTH(1-84) in healthy adult volunteer subjects of Japanese descent when exposed to single SC doses of rhPTH(1-84) at 25 μ g, 50 μ g, and 100 μ g.
- To compare the PD profile (serum calcium and phosphate levels) of a 100 μ g SC injection of rhPTH(1-84) in healthy adult volunteer subjects of Japanese descent and matched, non-Hispanic, healthy, adult Caucasian, subjects.
- To assess the PD profile (serum calcium and phosphate levels) of a 25 μ g and 50 μ g SC injection of rhPTH(1-84) in healthy adult volunteer subjects of Japanese descent.
- To assess the safety and tolerability of single SC doses of 25 μ g, 50 μ g, and 100 μ g of rhPTH(1-84) in healthy adult volunteer subjects of Japanese descent.

To evaluate the safety and tolerability of a 100 μ g SC injection of rhPTH(1-84) in matched, non-Hispanic, healthy, adult volunteer Caucasian subjects.

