9.8.3 Statistical Analysis of Pharmacodynamic Values

Individual values (original and baseline-adjusted) and PD parameters (original and baseline-adjusted) of serum total calcium, albumin-corrected calcium, phosphate and the calcium-phosphate (albumin-corrected calcium) product will be summarized with descriptive statistics (number, arithmetic mean, SD, CV%, median, minimum, maximum, geometric mean, and geometric CV%). Figures of individual and mean ($\pm SD$) concentration-time profiles of the original and baseline-adjusted PD markers, serum calcium (total and corrected for serum albumin) and phosphate, will be generated. Mean plots will be overlaid for the Japanese cohort and the Non-Japanese cohort. Box-Whisker plots for selected PD parameters will be prepared with the Japanese cohort and Non-Japanese cohort side by side.

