3.2 Secondary Objectives

- To assess the dose proportionality of the selected PK parameters of rhPTH(1-84) in healthy adult volunteer subjects of Japanese descent when exposed to single SC doses of rhPTH(1-84) at 25 μ g, 50 μ g, and 100 μ g.
- To compare the PD profile (serum calcium and phosphate concentration levels vs time) of a 100 μ g SC injection of rhPTH(1-84) in healthy adult volunteer subjects of Japanese descent and matched, non- Hispanic, healthy, adult Caucasian, subjects.
- To assess the PD profile (serum calcium and phosphate concentration levels vs time) of a 25 μ g and 50 μ g SC injection of rhPTH(1-84) in healthy adult volunteer subjects of Japanese descent.
- To assess the safety and tolerability of single SC doses of 25 μ g, 50 μ g, and 100 μ g of rhPTH(1-84) in healthy adult volunteer subjects of Japanese descent.
- To evaluate the safety and tolerability of a 100 μ g SC injection of rhPTH(1-84) in matched, non-Hispanic, healthy, adult volunteer Caucasian subjects.

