12.4.2 Baseline-adjusted Pharmacodynamic Data

Individual serum concentrations of PD markers, calcium (uncorrected and corrected for albumin), phosphate and calcium-phosphate product will be baseline-adjusted at each time point. Albumin-corrected calcium will be used to calculate the calcium-phosphate product. Baseline adjustment is subject- and dose-specific. For each subject, baseline is defined for each dosing period as follows: the baseline for Day 1 dosing is defined as the predose concentration on Day 1; the baseline for Day 4 dosing is defined as the predose concentration on Day 4; the baseline for Day 7 dosing is defined as the predose concentration on Day 7. Baseline-adjusted concentrations of PD markers are to be calculated by subtracting the appropriate baseline values from the original concentrations at each time point. If the baseline-adjusted concentration gives a negative value then the baseline-adjusted concentration should be set to zero.

Individual baseline-adjusted concentrations of serum total calcium, albumin-corrected calcium, phosphate and calcium-phosphate product will be listed and summarized with descriptive statistics (number, arithmetic mean, SD, CV%, median, minimum, maximum,) by ethnic group, dose and time point.

Figures of individual baseline-adjusted concentration-time profiles and mean (\pm SD) will be generated on linear scale for serum total calcium, albumin-corrected calcium, phosphate and calcium-phosphate product by ethnic group and dose. The mean plots will be created for the baseline-adjusted concentrations of the above four PD markers by overlaying all ethnic groups and doses on the same figure.

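### The plan sets out to compare calcium and phosphate response between the ethnic groups at 100 µg, but specifies no between-group estimate or interval and sets falls below baseline to zero

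*SAP*

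**What the plan says.** **Objective.** SAP section 3.2 sets the secondary objective "To compare the PD profile (serum calcium and phosphate concentration levels vs time) of a 100" µg injection in Japanese and matched Caucasian subjects. Protocol section 2.2.2 has the same objective: "To compare the PD profile (serum calcium and phosphate levels) of a 100" µg injection. The objective that follows it, for 25 and 50 µg in Japanese subjects alone, is only to assess the profile.

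**PD analysis.** Under SAP section 12.4.4 the PD parameters "will be listed and summarized with descriptive statistics" by ethnic group, dose and time point, and box plots of AUClast and Emax at 100 µg are drawn "with the Japanese cohort and Non-Japanese cohort side by side". SAP sections 12.4.1 and 12.4.2 add individual profiles and mean (±SD) profiles, the latter "overlaying all ethnic groups and doses on the same figure". Protocol section 9.8.3 is similar: descriptive statistics, box plots, and "Mean plots will be overlaid for the Japanese cohort and the Non-Japanese cohort".

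**Baseline adjustment.** SAP section 12.4.2 subtracts each subject's predose value for that dosing day and replaces any negative result by zero.

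**PK analysis, for contrast.** SAP section 12.3.4.2 compares the groups at 100 µg by an unpaired Welch's t-test on log-transformed PK parameters and reports a geometric mean ratio with a 90% CI. The exploratory dose-normalized PK comparisons get the same treatment.

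**The concern.** An objective to compare two groups is best met by an estimate of how far apart they are and how precisely that is known. The PD plan gives each group's distribution and leaves the comparison to the eye. The same SAP goes further for PK, and does so even for an objective it ranks as exploratory, so a secondary PD objective receives less than a lower-ranked PK one, with no reason given.

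The protocol's rationale for dose selection (section 3.2) expects no significant PK or PD difference between Japanese and non-Japanese subjects. Similar-looking plots from 12 subjects per group could be taken as bearing that out, without showing what difference the data still allow.

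The zero rule adds to this. It discards the size of any fall below baseline, and so distorts the baseline-adjusted Emax and AUClast of a marker that falls after dosing.

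**Working it through.** **1. Is a PD between-group estimate planned anywhere?** The places where one could appear are:

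- SAP sections 12.4.1 to 12.4.4 and protocol sections 9.8.2 and 9.8.3: no difference, ratio, interval or model for a PD parameter.
- SAP section 12.3.4.2: the Welch analysis names PK parameters only.
- SAP section 17 (changes from the protocol): no PD change. Protocol section 9.10: no other analyses.
- SAP section 20 (output list): PD tables 2.2.1 to 2.2.16 are all summaries, 0 of 16 with a between-group estimate. PD figures 2.2.1 to 2.2.20 are individual, mean and box plots, 0 of 20. The statistical appendices 2.1.7 to 2.1.10 are all PK, 0 of 4 for PD.
- By contrast, PK tables 2.1.7 to 2.1.9 and forest plot 2.1.12 give between-group results.

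The protocol and the SAP agree with each other. The gap starts in the protocol and the SAP carries it forward.

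**2. What does the zero rule do?** PD samples are taken predose and at 4, 8, 12 and 24 hours (SAP section 12.4.1). If all four post-dose values lie below the predose value, every baseline-adjusted value becomes zero, whatever the depth of the fall. Subjects with small and large falls then look alike. Falls are plausible: protocol section 1.2.2 reports that the drug significantly reduced the calcium-phosphate product in clinical trials. SAP section 12.4.3 defines Emax only as maximum effect and does not give its direction.

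Can signed change be recovered from the tables? Where falls occur, the baseline-adjusted summaries do not contain it. The original-scale summaries allow a mean change at one time point by subtracting mean predose from mean post-dose, if the same subjects contribute to both. They do not give the SD of that change, which depends on an untabulated within-subject correlation. The mean and SD of signed Emax and AUClast therefore cannot be recovered from the summaries.

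**3. How precise would the missing estimate be?** The plan has no figure to reproduce: SAP section 2.5 and protocol section 9.6 state that no formal sample size calculation was done.

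Inputs: n = 12 per group (SAP section 2.5); two-sided 90% level, as for PK (SAP section 12.3.4.2); SD assumed, because the documents give none.

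Half-width = t(0.95, df) × SD × √(1/12 + 1/12)

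- With equal variances, df = 22: 1.717 × √(2/12) = 1.717 × 0.408 = 0.70 SD.
- At the lowest Welch value, df = 11: 1.796 × 0.408 = 0.73 SD, with SD the root mean square of the two group SDs.

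For a change in calcium, at 0.70 SD:

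| Assumed SD (mmol/L) | 90% half-width (mmol/L) |
|---|---|
| 0.05 | 0.035 |
| 0.075 | 0.053 |
| 0.10 | 0.070 |

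The documents offer no basis for an equivalent phosphate range.

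**The case against.** The strongest defence is that the PD plan is coherent as a descriptive one. PK is the primary objective, the sample size rests on feasibility, and SAP section 2.6 calls the analyses exploratory. Comparison need not mean inference in these documents: protocol section 9.9.2 promises direct safety comparisons within a descriptive plan. The SAP follows the protocol, so nothing was dropped. The objective concerns a profile over time, and overlaid mean profiles address that directly.

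Much of this stands. It justifies having no hypothesis test and no multiplicity control. It does not explain the lack of an estimate with an interval, because the PK analyses have the same exploratory status and report one.

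Two stronger readings are tempting, and the documents do not support them.

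- A reader might infer that the plan handles 100 µg no differently from the lower doses. It does differ: the side-by-side box plots are specific to 100 µg.
- A reader might infer that the trial cannot answer its PD objective, or that the uncertainty is hidden altogether. Group n, mean and SD are tabulated, and individual concentrations and parameters are listed (Listings 5.7 to 5.9). An unadjusted difference on the original scale could be derived from the tables, and signed change from the listed concentrations. What is lost is prespecification: parameter, scale and confidence level would be chosen after the data were seen.

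**Conclusion.** The point holds as a moderate gap. A secondary objective to compare PD at 100 µg has no planned between-group estimate or interval in either document, and the zero rule removes falls from the baseline-adjusted parameters that such an estimate would naturally use.

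The precision of about 0.70 SD (up to 0.73 SD) rests only on 12 evaluable subjects per group and a 90% level. The conversion to ±0.035 to ±0.070 mmol/L for calcium rests on an assumed SD and is illustrative. A reader might divide it by the 0.125 to 0.175 mmol/L calcium rise in protocol section 2.1 to express it as a share of the effect. The documents do not support that: the rise is described as dose-related, in a passage on once-daily use in hypoparathyroidism, and is not tied to 100 µg in healthy volunteers.

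Nor should the consequence for dose selection be overstated. The synopsis says that the study's results will guide it, but gives the PD comparison no decision rule.

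**What to change.** In SAP section 12.4.4, for the 100 µg dose, prespecify the arithmetic Japanese-minus-Caucasian difference with a two-sided 90% CI for Emax and AUClast of albumin-corrected calcium, total calcium and phosphate, and label it exploratory.

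- **Method:** unpaired Welch on the untransformed scale. This keeps the PK test but not its log scale, since zero and negative changes cannot be logged. The SAP has no matched-pair PK analysis to carry over.
- **Data:** signed, untruncated change from baseline, with section 12.4.2 amended to match.
- **Definition:** state the direction of Emax for each marker, so that for phosphate it captures the largest fall.

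The signed-change parameters are not among those now planned, so the cost is a small re-derivation from the concentrations already collected, plus one table. No new samples or subjects are needed.

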13. OTHER ANALYSES

13.1 Quality of Life Analyses

Not applicable.

13.2 Health Economics and Outcomes Research Analyses

Not applicable.

14. INTERIM ANALYSIS

No formal interim analysis is planned for this study.

15. DATA MONITORING/REVIEW COMMITTEE

Not applicable, as no data monitoring review is planned for this study.

16. COMPUTER METHODS

Statistical analyses will be performed using Version 9.4 (or newer) of SAS® on a suitably qualified environment.

WinNonlin Phoenix version 6.3 or higher (Pharsight Corporation, Mountain View, California, USA) will be used for calculating PK and PD parameters.

17. CHANGES TO ANALYSES SPECIFIED IN PROTOCOL

Section 9.8.1.1 (Statistical Analysis of Pharmacokinetic Parameters) of the protocol states that:

Dose proportionality of PK parameters will also be examined for the Japanese subjects. Dose proportionality will be assessed for C_{max} and AUC (AUC_{last}) using the power model. The power model assumes a linear relationship between the natural log transformed parameter and the natural log transformed dose.

$$\ln(\text{Parameter}) = \alpha + \beta \times \ln(\text{Dose}) + \text{Random error}$$

In order to compare the PKs of rhPTH(1-84) between subjects of Japanese descent and matched non-Hispanic, Caucasian subjects, the differences of log-transformed PK parameters from the rhPTH(1-84) 100 μ g dose will be examined between groups using an analysis of variance model.

However, to take account of the different sequences, the dose proportionality of PK parameters will be assessed by the power model with more factors:

$$\ln(\text{Parameter}_{ijk}) = \alpha + \beta \times \ln(\text{Dose in } \mu\text{g}) + \pi_j + \gamma_k + \xi_{k(i)} + \varepsilon_{ijk} \quad (\text{Patterson and Jones, 2006})$$

Where α is the intercept, β is the slope, π_j and γ_i identify the period j of sequence i , $\xi_{k(i)}$ is the random-intercept accounting for each subject within sequence as their own control, and ε_{ijk} denotes within-subject error. Dose proportionality will be assessed by estimating mean slope with the corresponding two-sided 90% confidence interval (CI) from the power model.

For the comparison of PKs between subjects of Japanese descent and matched non-Hispanic, Caucasian subjects, the differences of log-transformed PK parameters from the rhPTH(1-84) 100 μ g dose will be examined between the two ethnic groups using Welch's t-test with Satterthwaite's approximation to the degrees of freedom, rather than by ANOVA as stated in the protocol. The reason for this method of comparison is that the variance in the two ethnic groups is not expected to be the same.

Table 1 Schedule of Assessments from protocol states that randomization takes place on Day 4 for subjects of Japanese descent. It is changed to be on Day 1 in Table 1 in SAP.

Table 3 Detailed Schedule of Assessments (Subjects of Japanese Descent) from protocol states that anti-PTH antibody sampling occurs at Predose 2 on Day 1, 4 and 7. However, it is not consistent with Table 1 in protocol. Therefore, "Anti-PTH antibody sampling on Day 1 only, not on Day 4 and 7" is added to the footnote e of Table 3 in SAP.

18. DATA HANDLING CONVENTIONS

18.1 General Data Reporting Conventions

Continuous variables will be summarized using the following descriptive statistics if not otherwise specified: n, mean, median, standard deviation, minimum, maximum. Categorical and count variables will be summarized by the number of subjects (n) and the percent of subjects in each category. Percentages will be presented to 1 decimal place.

The rules for the number of decimal places to present data and p-values are listed below:

1. For measures of median and mean, use 1 decimal place beyond those used for the measurement.
2. For measures of standard deviation and standard error, use 2 decimal places beyond those used for the measurement.
3. For measures of minimum and maximum values, use the same number of decimal places as those used for the measurement.
4. ≥ 5 is rounded up away from zero, whereas <5 is rounded down toward zero to account for rounding of negative numbers.
5. For p-values use 3 decimal places.
6. Presentation of p-values, display p-values that would round to 0.000 as <0.001.
7. BMI should be rounded to 1 decimal place for reporting.

18.2 Derived Efficacy Endpoints

Not applicable.

18.3 Repeated or Unscheduled Assessments of Safety Parameters

If a subject has repeated assessments before the start of investigational product, then the results from the final assessment made prior to the start of investigational product will be used as baseline. If post-baseline assessments are repeated, these will be captured as unscheduled visits, and the value recorded at the scheduled visit will be used for generating descriptive statistics. However, all post-baseline assessments will be used for PCI value determination and all assessments will be presented in the data listings.

18.4 Missing Date of Investigational Product

Since the investigational products will be administered during in-patient confinement at a CRC, there should not be any missing dates of investigational product.

18.5 Missing Date Information for Prior or Concomitant Medications

For prior or concomitant medications, incomplete (i.e., partially missing) start date and/or stop date will be imputed. When the start date and the stop date are both incomplete for a subject, impute the start date first.

18.5.1 Incomplete Start Date and Time

The following rules will be applied to impute the missing numerical fields. If the stop date is complete and the imputed start date is after the stop date, then the start date will be imputed using the stop date.

Missing day and month

- If the year of the incomplete start date is the same as the year of the date of the first dose of investigational product, then the day and month of the date of the first dose of investigational product will be assigned to the missing fields
- If the year of the incomplete start date is before the year of the date of the first dose of investigational product, then December 31 will be assigned to the missing fields
- If the year of the incomplete start date is after the year of the date of the first dose of investigational product, then 01 January will be assigned to the missing fields.

Missing month only

- The day will be treated as missing and both month and day will be replaced according to the above procedure.

Missing day only

- If the month and year of the incomplete start date are the same as the month and year of the date of the first dose of investigational product, then the day of the date of the first dose of investigational product will be assigned to the missing day
- If either the year is before the year of the date of the first dose of investigational product or if both years are the same but the month is before the month of the date of the first dose of investigational product, then the last day of the month will be assigned to the missing day
- If either the year is after the year of the date of the first dose of investigational product or if both years are the same but the month is after the month of the date of the first dose of investigational product, then the first day of the month will be assigned to the missing day.

Missing/Incomplete Time

- If the time is missing and the date is complete and is the same as the date of the first dose of investigational product, or the date is imputed to be this date, then the time will be set to the time of the first dose of investigational product. Otherwise, missing times will be imputed as 00:00.
- If the minutes are given but the hour is not, then the time will be regarded as completely missing and handled as above. If the hour is given but the minutes are not, then if the hour is the same as the hour of the first dose of investigational product, then the minutes of that

dose of investigational product will be assigned to the missing fields. Otherwise 00 will be assigned to the missing minutes.

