6.2.2 Dosing

After each subject has completed the screening process and found to be eligible to proceed to dosing (inclusive of all clinical laboratory values), the subject will be assigned a study cartridge, mixing device and injector pen and, following preparation of the study drug, will be administered a single dose of investigational product in the mid-thigh on the morning of Day 1 (for all study subjects) and Days 4 and 7 (for subjects of Japanese descent only). A detailed pharmacy manual will be provided that describes the materials to be used, the preparation of materials and administration of study drug.

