2. STUDY DESIGN

2.1 General Study Design

This study is a Phase 1, open-label, randomized, cross-over, single-center study to evaluate the PK and PD profiles and safety and tolerability of rhPTH(1-84) administered in healthy adult volunteer subjects of Japanese descent and matched non-Hispanic, Caucasian, healthy adult volunteer subjects. The non-Hispanic, Caucasian volunteers will receive a single dose of 100 μ g rhPTH(1-84). The Japanese subjects will receive 3 single doses of rhPTH(1-84). On Day 1 the subjects of Japanese descent will receive a single SC injection of 100 μ g. On Days 4 and 7 the subjects of Japanese descent will be randomized to receive a single SC injection of either 25 μ g or 50 μ g such that all of these subjects are exposed to the 3 dose strengths over a 7-day period to further characterize the PK profile in that group. A total of 24 subjects will be enrolled: 12 non-Hispanic, Caucasian subjects and 12 subjects of Japanese descent (1:1 male: female). Non-Hispanic, Caucasian subjects will be matched to Japanese subjects based on sex, age (± 7 years), and body mass index ($\pm 15\%$).

All subjects will receive a single dose of 100 μ g rhPTH(1-84) administered by SC injection in the mid-thigh with the Haselmeier injector pen on Day 1. In addition, the subjects of Japanese descent will also receive single dose injections of 25 μ g and 50 μ g rhPTH(1-84) administered by SC injection in the mid-thigh to characterize the PK profile over a range of doses. There will be a minimum of 72 hours (maximum 73 hours) washout between doses for the volunteers of Japanese descent. The study duration will comprise of a 28-day screening period, 1 treatment period for the non-Hispanic, Caucasian group (Days 1 and 2); 1 treatment period for the volunteers of Japanese descent (Days 1-8), and a follow-up visit (30 ± 2 days) after the last dose of investigation drug is administered for all subjects. The total number of nights subjects will be expected to stay at the clinical research center (CRC) is 2 for the non-Hispanic, Caucasian group and 8 for the volunteers of Japanese descent. The maximal total duration of study participation is 62 days for a non-Hispanic, Caucasian subject and 68 days for the volunteers of Japanese descent, if the maximum screening, treatment and follow-up visit durations are used.

Screening will occur within 28 days of the first dose. Subjects will be admitted to the CRC on Day -1.

Treatment Period:

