11.1 Adverse Events

Adverse events will be coded using Version 20.0 or newer of MedDRA.

An AE (classified by preferred term) that occurs during the study will be considered a TEAE if it has a start date/time on or after the first dose of investigational product or if it has a start date before the date of the first dose of investigational product, but increases in severity or intensity on or after the date/time of the first dose of investigational product. If more than 1 AE with the same preferred term is reported before the date of the first dose of investigational product, then the AE with the greatest severity will be used as the benchmark for comparison to the AEs occurring during the study under the preferred term. An AE that occurs after follow-up visit will not be counted as a TEAE. However, any SAE that occurs after the follow-up visit and is considered related should be counted as a TEAE.

Adverse events will be allocated to a dose by assigning them to the last dose taken at the time of the onset of the AE.

An overall summary of the number of subjects with TEAEs will be presented by ethnic group and dose at onset, including the number and percentage of subjects with any TEAEs, serious TEAEs, TEAEs related to investigational product, TEAEs leading to discontinuation of investigational product, severe TEAEs, and deaths.

The number and percentage of subjects reporting TEAEs for each ethnic group and dose at onset will be tabulated by system organ class (SOC) and preferred term; and by SOC, preferred term, and maximum severity. TEAEs considered related to investigational product will also be summarized by SOC and preferred term. If more than 1 AE occurs with the same preferred term for the same subject, then the subject will be counted only once for that preferred term using the most severe occurrence for the summarization by severity. Serious TEAEs and TEAEs leading to discontinuation of investigational product will be summarized by SOC, preferred term, ethnic group and dose at onset.

Listings will be produced for all AEs (including pre-treatment AEs), SAEs, AEs considered related to investigational product, AEs leading to discontinuation of investigational product, and deaths.

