18.6 Missing Date and Time Information for Adverse Events

For AEs, only incomplete (i.e., partially missing) start dates will be imputed. Incomplete stop dates will not be imputed.

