18.6.1 Incomplete Start Date and Time

Follow same rules as in Section 18.5.1.

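### An adverse event dated Day 4 or Day 7 with no clock time is placed before that morning's dose and charged to the previous one, even when it began afterwards

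*SAP*

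**What the plan says.** SAP 18.6.1 contains one instruction for incomplete AE start dates and times: "Follow same rules as in Section 18.5.1". Section 18.5.1 was written for prior and concomitant medications. Its time rule makes one exception, for a start date that "is the same as the date of the first dose of investigational product, or the date is imputed to be this date"; the time is then set to the time of that first dose. For all other dates, "Otherwise, missing times will be imputed as 00:00".

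The same section covers a recorded hour without minutes. If the hour matches the hour of the first dose, that dose's minutes are used; if not, the minutes become 00. This clause does not mention the date.

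SAP 11.1 then allocates AEs to doses "by assigning them to the last dose taken at the time of the onset of the AE", and the treatment-emergent tables are laid out by ethnic group and dose at onset.

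Japanese subjects receive 100 µg on Day 1, then 25 and 50 µg on Days 4 and 7 in randomized order (SAP 2.1 and 2.2). Protocol 6.2.2 puts all three doses in the morning. On spacing, SAP 2.1 says: "There will be a minimum of 72 hours (maximum 73 hours) washout between doses for the volunteers of Japanese descent". Caucasian subjects are dosed on Day 1 only.

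**The concern.** On Day 1 the SAP presumes that an untimed event followed the dose. On Days 4 and 7 the same rule presumes the opposite, and no reason is given. It reads as a single-dose convention applied to a group that is dosed three times.

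For medications this does little harm. SAP 9 lets one medication be concomitant with several doses, so an early imputed start does not remove it from the later dose. AE allocation is exclusive: an event charged to the earlier dose is lost from the later one.

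The by-dose AE tables are at stake, in particular the Japanese 100 µg column. Protocol 9.9.2 uses the 100 µg data for the direct safety comparison between the ethnic groups. Only the Japanese group has later dosing days, so any error in that comparison falls on one side.

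**Working it through.** The documents give no figure on this point, so the check applies the rules literally.

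**Completely missing time, complete date.** Apply SAP 18.5.1, then SAP 11.1:

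| AE date | Imputed time | Last dose at or before that time |
|---|---|---|
| Day 1 | Day 1 dose time | 100 µg |
| Day 4 | 00:00 | 100 µg (both sequences) |
| Day 5 | 00:00 | Day 4 dose (correct) |
| Day 7 | 00:00 | Day 4 dose: 25 µg in sequence 25/50, 50 µg in sequence 50/25 |
| Day 8 | 00:00 | Day 7 dose (correct) |

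The exact dosing hour is not given. The result was the same in all 24 combinations of six assumed Day 1 dosing hours (06:00 to 11:00), intervals of 72 or 73 hours, and the two sequences. It needs only that dosing comes after midnight.

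**How often the placement would be wrong.** Assume that onset is uniform over the calendar day. The share of untimed events that began after a dose given at hour *h* is 1 − *h*/24.

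- Day 1 dose at 06:00, 72-hour intervals: Days 4 and 7 both give 1 − 6/24 = 75%.
- Day 1 dose at 11:00, 73-hour intervals: the Day 4 dose falls at 12:00, 1 − 12/24 = 50%; the Day 7 dose falls at 13:00, 1 − 13/24 = 46%.

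The range is about 50–75% on Day 4 and 46–75% on Day 7. The low ends put the later doses past the morning that the Protocol specifies. The remaining events began before the dose and are placed correctly. For drug-related events the wrong share is probably higher, since Protocol 3.2 puts the PTH peaks at about 0.5 hours and 2–3 hours after a 100 µg dose.

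**Hour only.** Later doses come 72 to 73 hours after the previous one, so each falls at the same clock time or up to one hour later. Take a Day 4 dose at 09:20 and an AE recorded that day in the 09 hour with no minutes. The Day 1 dose was then between 08:20 and 09:20.

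- Day 1 dose at 08:40: the hours differ, so the AE becomes 09:00 and is charged to 100 µg.
- Day 1 dose at 09:10: the AE becomes 09:10 and is charged to 100 µg.
- Day 1 dose at 09:20: the AE becomes 09:20 and is charged to the Day 4 dose.

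An hour-only event in the dosing hour is thus put before the dose unless the imputed time equals that day's dose time.

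**Size in the tables.** With 12 Japanese subjects, one subject is 1/12 = 8.3 percentage points of a column. This is a maximum: SAP 11.1 counts a subject once per preferred term, so a subject already counted at 100 µg adds nothing.

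**The case against.** One textual defence is that SAP 18.6 opens with "For AEs, only incomplete (i.e., partially missing) start dates will be imputed", which mentions dates and not times. It does not help: the headings of 18.6 and 18.6.1 both include time, and the time rule in 18.5.1 expressly covers a complete date with no time.

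The stronger case is that the practical effect is small, and most of that stands. Japanese subjects are confined through Day 8, Protocol 9.2 has data checked for omissions and queried, and no document gives a rate of missing AE times. An event at 00:00 on Day 4 or 7 is still after the first dose, so treatment-emergent status does not change. SAP 2.6 calls the analyses exploratory, and all AEs are listed. Against this, missing times are plausible: Protocol 8.1.1 asks for start and stop dates and names no clock time, Protocol 7.2.2.3 elicits AEs with a general question about the time since the last visit, and the SAP itself provides for the case.

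A reader might infer more than the documents support:

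- That the rule empties the 25 and 50 µg columns. Only untimed events dated on the two later dosing days, and hour-only events in the dosing hour, can move. Events on Days 5, 6 and 8 and in follow-up stay where they belong.
- That every untimed event on those days is wrong. Those that began before the dose are right.
- That Day 7 errors reach the ethnic comparison. They move events between 25 and 50 µg, never into 100 µg.

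**Conclusion.** The plan contains a narrow error in an imputation convention. An untimed AE that began after the Day 4 dose is charged to 100 µg, and one that began after the Day 7 dose is charged to the Day 4 dose. Nothing elsewhere in the SAP or Protocol corrects this. An hour-only AE in the dosing hour can go wrong in the same way.

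The conclusion rests on morning dosing, which the Protocol states, and on a literal reading of SAP 18.5.1, 18.6.1 and 11.1. The shares of misplaced events rest on assumed dosing hours and uniform onset. The number of untimed events is unknown and probably small. The primary pharmacokinetic comparison is not touched. The point still merits correction because Day 4 errors can only raise the Japanese side of the 100 µg safety comparison, where the groups are small.

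**What to change.** Replace the cross-reference for times in SAP 18.6.1 with a rule for AEs only; incomplete dates can continue to follow 18.5.1:

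> If an AE start time is completely missing and the start date is the date of any dose, the time is set to the time of the dose given on that date; on any other date it is set to 00:00. If the hour is recorded without minutes, and the date and hour are those of a dose, that dose's minutes are used; in all other cases the recorded hour is kept and the minutes are set to 00.

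The last clause matters. A rule that ended in a blanket 00:00 would discard a known hour: an event recorded in the 14 hour on Day 4 would go back to midnight and be charged to 100 µg, whereas the present text places it correctly.

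The cost is a short addition to the SAP and a small change to the derivation; no new data are needed. The downside is that an untimed event that began before that morning's dose would be charged to that day's dose. The SAP already makes this presumption on Day 1.
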